7. PLANNED ANALYSIS

The format of the listings and tables will follow the BI guideline "Standards for Reporting of Clinical Trials and Project Summaries" (7).

The individual values of all subjects will be listed, sorted by dose group, subject number and visit. AE listings will be sorted by assigned treatment (see Section 7.8.1 below for details). The listings will be contained in an Appendix of the CTR.

For End-Of-Text tables, the set of summary statistics is: N / Mean / Standard Deviation (SD) / Min / Median/ Max. For tables that are provided for endpoints with some extreme data, median, quartiles and percentiles are preferred to mean, standard deviation, minimum and maximum. In general, means, medians, and percentiles are presented to one more decimal place than the raw data and SDs are presented to two more decimal places than the raw data. Minima and Maxima are presented to the same number of decimal places as the raw data.

Disposition of the patient population participating in the trial will be analyzed by treatment and presented by the categories in the standard CRF groups and presented in the clinical trial report as a frequency-distribution.

For categorical data, tabulations of frequencies will include all defined categories even if there is no count in a category. Tabulations of frequencies will display the number of observations in a category as well as the percentage (%) relative to the number of subjects in the respective treatment group. All patients in the respective patient set are used whether they have non-missing values or not, unless otherwise specified. Percentages will be rounded to one decimal place. The category missing will be displayed only if there are missing values.

If applicable, conversion from days to weeks, months and years will be as follows:

- weeks = days $\div 7$
- months = $12 \times \text{days} \div 365.25$
- years = days \div 365.25.

7.1 DEMOGRAPHIC AND OTHER BASELINE CHARACTERISTICS

Only standard descriptive statistics and summary tables are planned for this section of the report. Data will be summarised by treatment group and a "total" column will be included in the summary table.

7.2 CONCOMITANT DISEASES AND MEDICATION

Only descriptive statistics are planned for this section of the report.

Concomitant diseases (i.e., baseline conditions) will be coded similarly as AEs using the most recent version of MedDRA. A summary of concomitant diseases will be provided by treatment group, System Organ Class (SOC) and Preferred Term (PT). Concomitant diseases

c42059532-01

Proprietary confidential information © 2023 Boehringer Ingelheim International GmbH or one or more of its affiliated companies.

which are present at start of the study will be descriptively summarized by treatment, except for suicidal ideation, suicidal behavior and non-suicidal self-injurious behavior-. -These shall be removed from the concomitant diseases (baseline condition/medical history) and will be presented as a separate stand-alone table(s).

A medication/therapy will be considered concomitant to treatment if it (1) is ongoing at the start of randomized trial treatment or (2) starts within the on-treatment period (see Section 6.1 for a definition of study analysis phases). A medication/therapy will be considered as prior medication/therapy, if the end date of the medication/therapy is at any time prior to the start of randomized trial treatment.

Concomitant therapies (CTs) are coded according to WHO Drug Dictionary. CTs will be classified according to the Anatomical, Therapeutic, Chemical (ATC) classification system. The third ATC level will be used to categorize CTs by therapy type. In situations where a medical product may be used for more than one equally important indication, there are often several classification alternatives. As appropriate, subjects receiving CTs with more than one possible ATC level-three category will be counted more than once and footnote will clarify this possible multiple counting in tables. The most current MedDRA and WHO DD versions will be used.

7.3 TREATMENT COMPLIANCE

7.3.1 CRF Compliance

Only descriptive statistics are planned for this section of the report. Treatment compliance is calculated at Week 2, 4, 6, and 8(EOT) based on the CTP's flow chart.

Treatment Compliance = (number of tablets taken during a period) / (number of tablets that should have been taken during a period) * 100.

The cumulative treatment compliance during the entire treatment period is derived using the following examples:

For completers: if a subject's observed treatment compliance rates are 80%, 81%, 82%, 83%, at Weeks 2, 4, 6, and 8, then the cumulative treatment compliance percent = (.80*2 + .81*2 + .82*2 + .83*2)/8*100 = 81.5%.

For early discontinued subject: if a subject's observed treatment compliance rates are 80% at Week 2, 81% at Week 4, 50% at eEOT, then the cumulative treatment compliance rate = (0.80*2 + 0.81*2 + 0.5*((eEOT date - drug start date + 1)/7 - 4))/((eEOT date - drug start date + 1)/7) * 100% = 63.6% if the quantity (eEOT date - drug start date + 1) is assumed to be 36 days. In the example above the last regular visit is Week 4, so 4 is subtracted because there is compliance for the first 4 weeks. If the last regular visit is Week 2, then the '4' that's being subtracted would change to 2 to account for having compliance up through 2 weeks.

If at a particular visit a participant did not return the trial drug kits, then the compliance at that visit is zero.

Proprietary confidential information © 2023 Boehringer Ingelheim International GmbH or one or more of its affiliated companies.

Treatment compliance will be summarised overall and by visit for the treated set (FAS) using descriptive statistics (N, mean, SD, minimum, median, maximum). The number and percentage of patients with the following overall compliance categories will be presented using descriptive statistics (N, mean, SD, minimum, median, maximum). The number and percentage of patients with the following overall compliance categories will be presented:

- "<80% of planned",
- "80 to <100% of planned",
- ">=100% of planned",
- missing.

7.3.2 Video Confirmed

First, we define overall **and the second second second** (abbreviated as OAA), as the sum of all tablet adherence minus the total number of tablets flagged as red, orange, or yellow alerts, divided by a denominator of 3 times 56. Or, in other words:

- OAA = [[(Sum of all tablet adherence) (total number of red, orange, and yellow alerts)]/ 3*Treatment duration] *100,
 - Treatment duration is the number of days on treatment = treatment end date treatment start date +1
 - It is equal to 56 for subjects that adhere to the protocol.
 - 3 is the number of tablets per dose.

Tablet adherence is the successful administration of a pill as captured by **Red** alerts are tablet administrations for which the **Section** captures the dosing process, but includes strong visual proof of deceptive behaviors, non-adherence, and/or overdose of study drug. Examples include removing study drug from the mouth, 'cheeking', spitting out the drug, or using non-IP to dose. Also, in cases for which more than one pill was ingested simultaneously, a red alert is flagged. For orange alerts, the video captures the dosing process, but contains suggested visual proof of potentially deceptive behavior, potential nonadherence, or shows potential overdose of study drug. And lastly, for yellow alerts the video is missing visual information necessary to confirm adherence.

Note that tablet adherence is the administration of a tablet by the following method: visually confirmed by the

For subjects that discontinue treatment early, 56, which is the number of days from randomization to the planned treatment end, will be replaced by the total number of days from randomization to the respective date of early treatment discontinuation.

As defined in Section 6.4, the Adherent set (AS) consists of all subjects in FAS that achieved an OAA of at least 60%.

Proprietary confidential information © 2023 Boehringer Ingelheim International GmbH or one or more of its affiliated companies.

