Dose group	Number of tablets to be taken daily – in the morning 🌣			morning 🌣
Placebo	0	0	1	2
125 mg	1	2	0	0

During the COVID-19 pandemic, there might be situations that would not allow a patient to come to the site for the study visit. If the investigator judges it as acceptable and safe to continue trial medication, trial medication might be shipped from the site to the patient (for more details see section 6.1 and 10.3).

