6.4 SUBJECT SETS ANALYSED

The following analysis sets are defined for this trial:

- Screened Set (SS): consists of all subjects who signed informed consent.
- Treated Set (TS): consists of all subjects that have been randomized and that received at least one administration of study drug. The TS will be the main analysis set for the evaluation of safety. Subjects are analysed according to the actual received treatment.
- Full analysis set (FAS): consists of all subjects in TS that have a baseline and at least one evaluable post-baseline measurement for the primary endpoint. This is the main analysis set for the evaluation of efficacy data.
- Per protocol set (PPS): This is a subset of FAS, for subjects with adequate protocol compliance. It consists of all subjects in FAS without any important protocol deviations that impact efficacy assessments.

- Adherent set (AS): consists of all subjects in FAS that are at least 60% overall adherent to study medication. See Section 7.3.2 for further information.

c42059532-01

[figure not shown]
Proprietary confidential information © 2023 Boehringer Ingelheim International GmbH or one or more of its affiliated companies.

Table 6.4: 1 Subject sets analyzed

	Subject set					
Class of analyses	TS	SS	FAS	PPS	PKS	AS
Primary and secondary endpoints, compliance			Х	X*		
Further endpoints (Х			
Disposition		Х				
					Х	
Safety variables and iPDs	Х					
Demographics, baseline characteristics, exposure	Х			(X)		
Primary endpoint adjusted for overall study						Х

* If the percentage of subjects in FAS with iPD that lead to the exclusion from the PPS is > 10%, then sensitivity analysis of the primary and secondary efficacy endpoints using PPS may be conducted.

(X) An additional PPS presentation of the demographic/baseline endpoints may be provided in the End of Text (EoT) section, if there are a non-negligible number of treated subjects with no post randomization data for the primary endpoint.

Proprietary confidential information © 2023 Boehringer Ingelheim International GmbH or one or more of its affiliated companies.

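### The video adherence score red-flags swallowing more than one tablet at once although the scheduled dose is three, and leaves the alert count undefined, so a fully dosed patient can fall in or out of the Adherent Set

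*SAP*

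**What the plan says.** SAP 7.3.2 defines overall adherence (OAA) in prose "as the sum of all tablet adherence minus the total number of tablets flagged as red, orange, or yellow alerts", over a denominator of 3 × 56. It explains that "3 is the number of tablets per dose" and says of treatment duration that "It is equal to 56 for subjects that adhere to the protocol". The bullet formula beside the prose counts alerts rather than flagged tablets.

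Red alerts are for strong visual proof of deception, non-adherence or overdose. The same paragraph adds: "in cases for which more than one pill was ingested simultaneously, a red alert is flagged". No exception is made for the scheduled dose. At the other end of the scale, "for yellow alerts the video is missing visual information necessary to confirm adherence". Tablet adherence itself means a successful administration that was visually confirmed; part of that definition is redacted.

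OAA alone decides membership of the Adherent Set, which "consists of all subjects in FAS that are at least 60% overall adherent to study medication" (SAP 6.4). SAP Table 6.4:1 assigns an analysis of the primary endpoint to this set.

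Protocol Table 4.1.4:1, headed "Number of tablets to be taken daily – in the morning", lists one 25 mg and two 50 mg tablets, or the matching placebos. The text of Protocol 4.1.4 asks for intake by mouth with water, consistently with respect to food, at about the same time each morning. Protocol 5.8.3 has patients follow set steps in front of the camera, but the readable text does not list them.

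**The concern.** A three-tablet dose swallowed in one go breaks no readable dosing instruction, yet the SAP gives it the same alert colour as spitting the drug out. The alert is then subtracted, so tablets seen to be swallowed can score as not taken.

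Two definitions that decide the size of the effect are missing. One is the unit of an alert: the prose counts tablets, the bullet formula counts alerts. The other is whether a flagged tablet is also in the adherence sum. For yellow alerts this matters most. Such a tablet is by definition not confirmable, so on the SAP's own wording it need not be in the sum, and subtracting it would then penalise it a second time.

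At stake is what the Adherent Set means. It is presented as the patients who took at least 60% of their medication. As written, membership can turn on swallowing habit, on video quality, or on how the programmer reads the rule.

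**Working it through.** The documents give no worked OAA value to reproduce. Their building blocks agree: Day 1 to Day 56 is 56 − 1 + 1 = 56 days, 3 × 56 = 168 tablets, and full dosing without alerts gives 168/168 = 100%.

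**Inputs.** Three tablets per dose, 56 days, prose and bullet formulas, alert definitions (SAP 7.3.2); 60% cut (SAP 6.4 and 7.3.2); 1 + 2 tablets each morning in both arms (Protocol Table 4.1.4:1).

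**Formula.** OAA = 100 × (adherent tablets − alerts) / (3 × days on treatment). The bullet formula is read as a subtraction, as in the prose.

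**Case 1: all three tablets swallowed together on all 56 days, every tablet taken.**

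| Reading | OAA | Days of joint swallowing that first give OAA < 60% |
|---|---|---|
| (a) alert per tablet, tablets in the sum | (168 − 168)/168 = 0% | 23 |
| (b) alert per tablet, tablets not in the sum | (0 − 168)/168 = −100% | 12 |
| (c) alert per dosing event, tablets in the sum | (168 − 56)/168 = 66.7% | never |
| (d) alert per dosing event, tablets not in the sum | (0 − 56)/168 = −33.3% | 17 |

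The day counts, with the remaining days clean:

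- (a) 22 days: (168 − 66)/168 = 60.7%; 23 days: (168 − 69)/168 = 58.9%.
- (b) 11 days: (135 − 33)/168 = 60.7%; 12 days: (132 − 36)/168 = 57.1%.
- (d) 16 days: (120 − 16)/168 = 61.9%; 17 days: (117 − 17)/168 = 59.5%.

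Two tablets together and one separately every day gives (168 − 112)/168 = 33.3% under (a).

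**Case 2: yellow alerts, if such tablets are not in the sum.** With 118 tablets confirmed and 50 yellow, OAA = (118 − 50)/168 = 40.5%, although 118/168 = 70.2% were confirmed. If a share c is confirmed and all the rest carry an alert, OAA = c − (1 − c) = 2c − 1. The 60% cut then needs c ≥ 80%, and OAA is negative when c is below 50%. If yellow tablets are in the sum, each is removed once and this penalty does not arise.

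**With joint swallowing of the scheduled tablets not counted against the patient**, Case 1 gives (168 − 0)/168 = 100%.

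**The case against.** The strongest reply is that the rule may be deliberate. The app's intake steps, the vendor training at Visit 1A and the manuals in the site file are not in the readable text, and parts of SAP 7.3.2 and Protocol 5.8.3 are redacted. If patients are told to take tablets one by one on camera, flagging joint swallowing is a verification rule. A three-tablet morning dose is compatible with swallowing one after another; a reader might infer that the protocol tells patients to take the tablets together, but it does not. This stands as a limit on how often the problem would occur. It does not remove the problem: a visibly ingested scheduled tablet would still be scored as not taken, and no such instruction is cross-referenced in the SAP.

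It is also fair that subtraction is correct bookkeeping when flagged tablets are in the sum, since each tablet then scores 0 or 1. The description of red alerts as administrations caught on video gives that reading some support. It follows that the 0% and 40.5% results rest on opposite readings and cannot be added up as two established errors. The 80% figure also needs every unconfirmed tablet to carry an alert, whereas a missed dose without a video may carry none.

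Finally, video monitoring is exploratory (Protocol 4.3), tablet-count compliance is reported separately (SAP 7.3.1), and the trial has no formal hypothesis test (Protocol 7.1). This bounds the importance of the point.

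**Conclusion.** The point holds as a defect in the derivation of OAA. On the SAP's prose, with flagged tablets in the sum, a patient who takes every scheduled tablet on camera can score 0%, and 23 or more days of joint swallowing out of 56 remove that patient from the Adherent Set. Of the four readings of the undefined terms, three exclude the everyday case and one keeps it at 66.7%. The yellow-alert double penalty and negative scores are conditional on those tablets being outside the sum, which the SAP leaves open.

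Three stronger conclusions are not supported. One is that fully dosed patients will be excluded: 0% is the worst case, and no document gives a frequency of joint swallowing. Another is that the primary result is affected: SAP 7.4.1 uses the FAS. The third is that the Adherent Set analysis cannot show whether the effect depends on exposure: its row in Table 6.4:1 is incomplete and no readable section describes it, so only misclassification of its members can be claimed.

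The conclusion assumes that no redacted or external instruction already settles the counting unit or exempts the scheduled dose.

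**What to change.** Before treatment information is released, redefine the score in SAP 7.3.2 so that each scheduled tablet counts 0 or 1:

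- OAA = (tablets visually confirmed as ingested and carrying no red or orange alert) / (3 × days on treatment) × 100.
- Yellow-alert tablets score 0, with no further subtraction.
- For this score, swallowing no more than the day's scheduled tablets together is not counted as non-adherence when ingestion is visible.
- The tablet is the stated unit in both the prose and the formula.

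The score then stays between 0% and 100%, and the 60% cut means what SAP 6.4 says. The alert rule, the three-tablet schedule and the app's intake instructions should be reconciled, with a cross-reference in the SAP.

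The cost is a change of wording and a small derivation change. It needs the vendor to supply the reason for each alert, which is an assumption because the documents describe alert colours and examples but not stored reasons. Verification of individual tablets becomes somewhat weaker when they are taken together. Compared with the per-tablet readings (a) and (b), the Adherent Set can only stay the same size or grow.

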7.4 PRIMARY OBJECTIVE ANALYSIS

7.4.1 Main analysis

The primary endpoint is the change from baseline to Week 8 in CAPS-5 total score. Baseline refers to the measurement recorded at randomization (Visit 2), if data at Visit 2 is missing, then data from Visit 1 will be considered baseline. The primary analysis of the primary endpoint will use a hybrid estimand that combines the treatment policy and hypothetical estimands as detailed in Section 6.3.

MMRM analysis

The change from baseline in CAPS-5 total score at Week 8 for each dose group as well as the corresponding variance-covariance matrix are estimated by a mixed effects model repeated measure (MMRM) including the fixed categorical covariates of treatment, and the stratification indicator of presence of significant childhood trauma (yes vs. no), the continuous fixed covariates of baseline CAPS-5 total severity score and time since index event (in years) and the treatment-by-visit interaction. Patient is considered as a random effect. Visit will be treated as a repeated measure with an unstructured covariance matrix used to model the within subject variability. The Kenward-Roger approximation will be used to estimate the denominator degrees of freedom. Analyses will be implemented using SAS 9.4 PROC MIXED. FAS is used for the primary analysis of the primary efficacy endpoint.

More specifically, the change in CAPS-5 total score from baseline (Visit 2), at Visits 2, 6, and 10 (Weeks 0, 4, and 8) will be evaluated using an MMRM accounting for the following sources of variation: 'treatment', 'visit', 'presence of significant childhood trauma (yes vs.no), time since index event (in years) and 'baseline CAPS-5 total score' as continuous covariates, and treatment-by-visit interaction, as well as the random 'subject' effect. The methods described in Section 10.1 will be utilized to resolve model non-convergence.

SAS code for MMRM:

The following SAS code will be used to calculate the MMRM.

PROC MIXED DATA=indata cl method=reml;

CLASS visit trt stratum subject;' MODEL ept = stratum visit*trt time_since_index base / ddfm=kr s CL; REPEATED visit / subject= subject type=un r rcorr; LSMEANS visit*trt / pdiff=all om cl alpha=**0.05** slice=visit;

RUN;

Results of the MMRM (N, mean, SE and 95% CI per dose group and timepoint) will be presented in tables and displayed graphically.

c42059532-01

Proprietary confidential information © 2023 Boehringer Ingelheim International GmbH or one or more of its affiliated companies.

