Day	-28 c V anytir to 8 befor	l A ne up days	13	8±2	15±2	22±2	29±2	36±2	43±2	50±2	57+2		EOT / (Early drug discon- tinuation date) plus 28+2 days	
Additional Patient Asses	sments/P	rocedur	es											
Patient informational video placebo response mitigation ⁷		х												5 min
Patient training video speech recording ⁷		х												5 min
Training on Smartphone App ⁸		х												10-15 min
Drug intake adherence monitoring ⁹					← all IN	MP intake	at clinica	al site and	at home)				5 min
EcMA assessments ¹⁰				← perf		-	weekly fo				5-10 min			

Boehringer Ingelheim BI Trial No.: 1402-0030 c34993667-05 Clinical Trial Protocol

09 Jun 2023

Page 16 of 148

Proprietary confidential information © 2023 Boehringer Ingelheim International GmbH or one or more of its affiliated companies

At the screening visit, all clinical examinations and procedures as per Flow Chart 1 should be performed first, followed by PCL-5 (version comprising LEC, Extended Criterion A and PCL5),CAPS-5 and MINI, followed by the other clinical outcome assessments, listed in Flow Chart 2. Blood draws are preferably done after clinical outcome assessments and procedures is described in detail in section 6.2.

For all further clinical visits, please refer to section 6.2.2 for details on order of assessments and procedures.

- 1 Eligibility of patients is to be confirmed before Visit 1A is scheduled. Visit 1A must be scheduled at minimum 8 days prior to V2 to allow for 7 days of EcMA assessments before randomization. The randomization visit V2 should be planned shortly (preferably within the same week) after completion of the 7 day EcMA baseline assessment period.
- 2 Visits 3, 5, 7 and 9 will be conducted via telephone or by video call, if in line with local regulation.
- 3 Day of Randomisation / Day of first intake of randomized medication all activities, except postdose PK sampling, should be done before drug administration. For exceptions please refer to section 6.2.2.
- 4 The CAPS-5 past month version will be used at the screening visit for PTSD diagnosis and eligibility assessment. At the randomization visit V2 and at all subsequent study visits, the CAPS-5 past week version will be used.
- 5 C-SSRS: Columbia Suicide Severity Rating Scale baseline/screening version used at Screening, Columbia Suicide Severity Rating Scale since-last-visit version used for all subsequent study visits

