5.2 ASSESSMENT OF EFFICACY

5.2.1 Clinician administered assessments

In addition to confirmation of PTSD diagnosis, using the CAPS-5 past month version, the CAPS-5 past week version will be used to assess PTSD total symptom severity as well as cluster symptom severity at Baseline and during the course of the trial.

CAPS-5 - Clinician-Administered PTSD Scale for DSM-5

The Clinician-Administered PTSD Scale for DSM-5 (CAPS-5) is a 30-item structured interview designed to make a current and lifetime diagnosis of PTSD evaluating the past month period as well as to assess PTSD symptoms over the past month or past week, depending on the version used. [R21-2327, R21-0830, R21-2548].

In addition to assessing the 20 DSM-5 PTSD symptoms, questions target the onset and duration of symptoms, subjective distress, impact of symptoms on social and occupational functioning, improvement in symptoms since a previous CAPS administration, overall response validity, overall PTSD severity, and specifications for the dissociative subtype (depersonalization and derealization). Administration requires identification of an index traumatic event to serve as the basis for symptom inquiry.

Each of the 20 symptom items is rated on a 5-point severity rating scale ranging from 0 (absent) to 4 (extreme/incapacitating) with a single severity score combining information about frequency/amount and intensity according to detailed scoring rules. A CAPS-5 total symptom severity score is yield by summing individual item scores. The total severity score ranges from 0 to 80 with higher scores indicating higher symptom severity.

CAPS-5 symptom cluster severity scores are yield by summing individual item scores pertaining to the following clusters (sometimes also referred to as domain): Criterion B (reexperiencing), Criterion C (avoidance), Criterion D (negative alterations in cognitions and mood) and Criterion E (hyperarousal). A symptom cluster can also be calculated for dissociation by summing scores for items 29 and 30.

Two formats of the CAPS-5 measure will be used in this trial:

- CAPS-5 past month version for confirmation of PTSD diagnosis and evaluation of eligibility (for screening visit only) [R21-2327].
- CAPS-5 past week version for efficacy measurement (all subsequent trial visits) [R21-2548].

The CAPS was designed to be administered by trained clinicians. The full interview takes 45-60 minutes to administer.

Page 64 of 148

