7.2 PLANNED ANALYSES

7.2.1 General considerations

The following patient analysis sets are defined for this trial:

- Full Analysis Set (FAS): includes all randomized patients who received at least one
 dose of trial medication during the trial and had a baseline and at least one postbaseline observation for the primary or secondary endpoints. The FAS is used for
 efficacy analyses and patients in FAS are analysed under the randomized trial
 medication.
- Treated Set (TS): includes all patients who signed informed consent and were treated with at least one dose of the trial medication. Patients in TS are analyzed under the actual trial medication received at randomization. The TS is used for safety analyses as well as demographics and baseline characteristics.

Data from patients who were screened but not randomized will be listed but not included in any summary or inferential statistics.

In general, baseline values are the last measurements taken prior to the first administration of trial medication at randomization (Visit 2), (see Flow Chart 1). Further details (e.g., the handling of randomized patients that receive the wrong treatment) will be provided in the TSAP.

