6.7 BASELINE, TIME WINDOWS AND CALCULATED VISITS

Baseline is defined as the last observation at, or prior to Visit 2. Hence, if a subject is randomized at Visit 2, but does not start trial medication until a future visit (e.g., Visit 4), then his/her baseline is the latest assessment performed at Visit 2. However, for laboratory safety measurements, the last value prior to the first drug administration will be considered as the baseline value.

Planned and actual test days are included in the analysis data sets and are calculated relative to the beginning of treatment as indicated in Table 6.7: 1 below.

For efficacy measurements, only one observation per time window will be selected for statistical analysis –the first one in the corresponding time window. If there are two observations which have the same difference in days to the planned day, or if there are two observations on the same day, the first value will be selected. If an observation is available on the last day of treatment, this observation will be preferably selected over any later observation that is still within the time window. Assignment of efficacy observations to visits based on time windows will be based on the non-imputed (observed) data. Repeated and unscheduled efficacy measurements will be assigned to the nominal visits according to the time windows described in Table 6.7: 1.

For safety measurements, data collected at all visits will be used. For repeated and unscheduled safety measurements for the same visit on treatment, the worst of these will be selected for analysis. In the case for which there is no standard reference direction for the safety parameter, the average of all values for the same visit will be used for analysis.

Visit	Relative to treatment start	
	Planned test day	Actual test day
2	1	Day 1 – Day 2

Table 6.7: 1Planned and actual study days

c42059532-01

Proprietary confidential information © 2023 Boehringer Ingelheim International GmbH or one or more of its affiliated companies.

3	8	Day 3 – Day 12
4	15	Day 13 – Day 19
5	22	Day 20 – Day 26
6	29	Day 27 – Day 33
7	36	Day 34 – Day 40
8	43	Day 41 – Day 47
9	50	Day 48 – Day 52
10/EOT	57 for completed subjects	Day 53 – treatment stop date (stopdt) + 7 days
eEOT	N/A (for early discontinued subjects)	Date of the last administration of trial medication + 7 days (for early discontinued subjects).

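### Does falling back on the Visit 1 past-month CAPS-5 as baseline, when Visit 2 is missing, damage the primary analysis?

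*SAP*

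**What the plan says.** **SAP.** Section 7.4.1 sets the CAPS-5 baseline at Visit 2 and provides that "if data at Visit 2 is missing, then data from Visit 1 will be considered baseline". Section 6.7 leads to the same place: "Baseline is defined as the last observation at, or prior to Visit 2". For a patient who starts treatment late, 6.7 holds the baseline at randomisation: "then his/her baseline is the latest assessment performed at Visit 2". Neither section mentions the recall period.

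**Protocol, general rule.** Section 7.2.1 states: "In general, baseline values are the last measurements taken prior to the first administration of trial medication at randomization (Visit 2"). It leaves further detail to the SAP.

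**Protocol, form of the interview.** Section 5.2.1 lists the "CAPS-5 past month version for confirmation of PTSD diagnosis and evaluation of eligibility (for screening visit only"), and says "the CAPS-5 past week version will be used to assess PTSD total symptom severity as well as cluster symptom severity at Baseline". Flow Chart 2, footnote 4, agrees: "At the randomization visit V2 and at all subsequent study visits, the CAPS-5 past week version will be used".

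**Analysis set.** The SAP's full analysis set (6.4) "consists of all subjects in TS that have a baseline and at least one evaluable post-baseline measurement for the primary endpoint". Whether a patient has a CAPS-5 baseline therefore decides whether that patient is analysed for efficacy at all.

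**The concern.** The two scores measure different things. Visit 1A comes after Visit 1 and at least 8 days before Visit 2, so a past-week rating at Visit 2 shares no rated day with the Visit 1 interview. Visit 1 may lie up to 28 days before the first dose. The Visit 1 score is also the one on which patients were selected (at least 30), so it carries regression to the mean.

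The same baseline feeds the change score, the model covariate and the denominators of the 30% and 50% response endpoints. One patient shows the effect, with illustrative scores: a Week 8 score of 29 is a reduction of (40 - 29)/40 = 27.5% from a Visit 2 score of 40, a non-responder, but (45 - 29)/45 = 35.6% from a Visit 1 score of 45, a responder. Protocol 5.2.1 names the past-week form at Baseline, so the fallback looks like a departure from the protocol on the primary endpoint.

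**Working it through.** **1. Is there a contradiction?** Protocol 7.2.1 is a general rule that admits the last pre-dose score, which is Visit 1 when Visit 2 is missing. Protocol 5.2.1 and footnote 4 say which form is administered at which visit; they give no rule for a missing Visit 2 score. The SAP supplies one. The recall period is left unaddressed, but the SAP does not overturn a protocol rule.

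**2. How often, and in which arm?** Protocol 6.2.2 places the first dose after the Visit 2 assessments, apart from the remaining patient-reported scales and optional speech recordings. It puts CAPS-5 second in the outcome order, after PCL-5. A patient dosed without a Visit 2 CAPS-5 should be rare, and the omission comes before treatment under blinding, so the arms can differ only by chance.

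**3. Assumed inputs.** The documents give none of these: unselected past-month mean 36 to 42, SD 8 to 10, correlation r between visits 0.6 to 0.8, gap g (past-month minus past-week) -6 to +6 points, 2% or 5% of patients affected.

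**4. Regression to the mean** = (mean of a normal truncated at 30, minus the population mean) x (1 - r).
- Mean 42, SD 8, r 0.8: 1.11 x 0.2 = 0.22 points.
- Mean 36, SD 10, r 0.6: 4.59 x 0.4 = 1.84 points.

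**5. Shift in an arm's mean change** = -(share affected) x (g + regression to the mean).

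| Setting | 2% affected | 5% affected |
|---|---|---|
| g = -6, mean 42 | -0.02 x (-6 + 0.22) = +0.12 | -0.05 x (-5.78) = +0.29 |
| g = -6, mean 36 | -0.02 x (-6 + 1.84) = +0.08 | -0.05 x (-4.16) = +0.21 |
| g = +6, mean 36 | -0.02 x (6 + 1.84) = -0.16 | -0.05 x 7.84 = -0.39 |

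This shift is common to both arms in expectation.

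**6. Response status.** By simulation, the status of an affected patient differs from the one a Visit 2 baseline would give in 8.6% to 16.4% of cases for the 30% criterion and 4.4% to 13.5% for the 50% criterion. With 100 evaluable per arm (Protocol 7.5), the range is 2 x 0.044 = 0.09 to 2 x 0.164 = 0.33 patients per arm at 2% affected, and 5 x 0.044 = 0.22 to 5 x 0.164 = 0.82 at 5%.

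**7. Treatment contrast.** With baseline as a covariate, modelling Week 8 change gives the same treatment contrast as modelling the Week 8 score: subtracting the baseline only alters its own coefficient. The substituted value therefore acts through the covariate alone. A simulation used 100 per arm, 8,000 runs per scenario, mean 36, SD 10, r 0.6, Week 8 noise SD 12, effect 0.35 x 12 = 4.2 before scores are clipped to 0-80, missingness independent of arm, and covariance analysis at Week 8. At 5% affected:

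| Gap | No missing | Fallback | Excluded | SD, fallback | SD, excluded |
|---|---|---|---|---|---|
| -6 | -4.135 | -4.132 | -4.139 | 1.706 | 1.720 |
| 0 | -4.035 | -4.034 | -4.043 | 1.664 | 1.693 |
| +6 | -3.855 | -3.853 | -3.852 | 1.595 | 1.606 |

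The fallback differs from the complete-data result by 0.003, 0.001 and 0.002 points; exclusion differs by 0.004, 0.008 and 0.003. The largest difference for the fallback over ten scenarios (2% and 5% affected, five gaps) was 0.008. Exclusion raises the SD here by 1.720/1.706 = 0.8%, 1.693/1.664 = 1.7% and 1.606/1.595 = 0.7%. Across the assumed inputs at 5% affected, the increase runs from nothing to about 2.4%.

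**The case for a change.** The strongest case for a change is that it would be cheap. A sentence reserving the CAPS-5 baseline for the past-week score would make every individual change and response value refer to one recall period and settle the matter before unblinding. Because Protocol 7.2.1 speaks only in general terms, no protocol amendment would be needed. It is also true that the numbers above rest on assumptions, and that the contrast simulation uses one setting of mean, SD and correlation with a Week 8 covariance analysis in place of the planned repeated-measures model.

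What stands is that a patient on the fallback has a less clean change score and may be misclassified as a responder or non-responder. The remedy costs those patients more, however. The fallback gives the same response status as a Visit 2 score in roughly 84% to 96% of them; without a baseline they have no status, because SAP 6.6 does not impute missing response. Under SAP 6.4 they would also leave the full analysis set, and with it the PCL-5 analysis. The protocol defines that set on primary or secondary endpoints, but this wording difference is a separate matter.

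If the arms happened to differ in how many patients use the fallback, an unadjusted difference in mean change would move by the gap times the difference in shares: 2 x 0.02 = 0.04 up to 8 x 0.05 = 0.4 points for assumed gaps of 2 to 8 points and differences of 2 to 5 percentage points. Since the omission precedes dosing, such a difference would be chance and not bias.

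**Conclusion.** The mixing of recall periods is real, but no change is called for. The SAP states in advance a workable rule for a case that should be rare, and the protocol's general rule admits it. Keeping a treated patient with a slightly mismatched covariate, or dropping that patient to keep the scale uniform, is a fair trade-off; the SAP's choice is the one many statisticians would make. Under the assumed inputs it costs less than half a point in an arm's mean change and fewer than one altered response per 100 patients in an arm at 5% affected. The simulated contrast moves by at most 0.008 points against a standard deviation of the estimate near 1.6 to 1.7. The proof-of-concept conclusion is unaffected, and Protocol 7.1 plans no formal hypothesis test.

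The conclusion rests on missing Visit 2 scores being few and unrelated to arm, which the order of procedures at Visit 2 supports. SAP Section 7 lists individual values by patient and visit, so anyone analysed on a Visit 1 baseline can be identified, counted and footnoted in the report. Parts of the SAP are not visible, so nothing is claimed about what its sensitivity analyses cover.
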